### 13.5 Storage of GS010 and Placebo

GS010 and Placebo are stored at  $\leq -70^{\circ}\text{C}$  in a freezer under the supervision of the study pharmacist or the Investigator. Vials of GS010 and Placebo will only be dispensed with the written authorization of the Investigator or a specifically designated delegate of the Investigator. Please refer to the Pharmacy Manual for full details.

### 13.6 Packaging and Labeling

GS010 and the Placebo are individually packaged as directed in the IMPD.

The GS010 package contains one vial of GS010.

The placebo package contains one vial of placebo.

The primary label on the vial as well as secondary container labeling is in the country-specific language for each site. The labels are compliant with local regulatory requirements. The primary and secondary packaging together comply with the labeling requirements.

Packaging of IMPs will be compliant with the International Air Transport Association (IATA) regulation for genetically modified organisms.

### 13.7 Dose and Administration

Please refer to the Intravitreal GS010/Placebo Injection Guide, for full details.

#### 13.7.1 IMP GS010

GS010 will be administered via standard intravitreal injection under local (i.e. topical) anesthesia. Any eye allocated to treatment with GS010 will receive a single IVT injection of the IMP. GS010 will be administered per the study schedule. GS010 will be administered at a dose of [REDACTED] /eye in a final volume of [REDACTED].

#### 13.7.2 IMP Placebo

The placebo will be administered via standard intravitreal injection, under local (i.e. topical) anesthesia. Any eye allocated to placebo will receive a single IVT injection of placebo. The placebo

will be administered per the study schedule. The placebo will be administered in a final volume of [REDACTED].

### 13.8 Dispensing and Accountability

The IMPs (GS010 and placebo) will only be dispensed, per the Investigator's prescription, to eligible subjects who meet all selection/non-selection and inclusion/exclusion criteria and according to the study schedule and treatment scheme.

The IMPs (GS010 and placebo) will be tracked during the handling process from prescription to destruction (through dispensation, reconstitution, administration and decontamination).

Accountability for GS010 and placebo is the responsibility of the Investigator. This responsibility however may be delegated to the Pharmacist(s). This delegation will be documented in the Site Trial Master file.

The Pharmacist or the person responsible for study medication management will keep an IMPs accountability log detailing the dates, batch number and quantity dispensed for each subject. Accountability records will be verified by the study monitor during site visits.

At the end of the study, all unused vials of the IMPs (GS010 and placebo) will be destroyed at the investigation center following internal procedures for Genetically Modified Organisms (GMO). A copy of the certificate of destruction should be made available to the sponsor.

### 13.9 Prior and Concomitant Therapies

Prior therapy is defined as prescription and non-prescription medications and preparations, including health and/or dietary supplements taken within 30 days prior to signing the informed consent, but discontinued prior to signing informed consent.

Concomitant therapy is defined as prescription and non-prescription medications and preparations, health and/or dietary supplements other than GS010 that the subject receives during the study (i.e. any time after the signing of informed consent). This includes any medication started prior to signing informed consent and continued after signing the informed consent form.

Idebenone must be discontinued at least seven days prior to Inclusion Visit 2 and is not allowed to be taken during the study period. No other medications are specifically forbidden during the study.

#### 13.9.1 Immune Modulating Regimen

All subjects will receive a peri-treatment systemic oral immune modulating regimen for the prevention or diminution of ocular inflammation related to IVT injection of GS010. The immune modulating regimen will consist of oral corticosteroid starting 2-days prior to the initial treatment administration to any eye of the subject and will be completed after a 28-day immune modulating regimen. The following regimen will be administered:

- Immune modulating agent: corticosteroid
- Route of administration: per os (p.o.; i.e. orally)
- Administration regimen:

- 40 milligrams (mg) daily for 1 week, starting two days prior to treatment administration to any eye of the subject, then
- 30 mg daily for 1 week, then
- 20 mg daily for 1 week, then
- 10 mg daily for one week → then stop

### 13.10 Method of Assigning Treatment

An IRS will be utilized to enroll and randomize subjects. Each subject will receive a unique subject identification number assigned at Screening Visit (Visit 1), which will serve as the subject identifier throughout the study. The subject number will be required for all communication between the Investigator (or designee) and the IRS. Subject numbers will be tracked via the IRS. Subjects who meet all selection and inclusion criteria will then be randomized via the IRS, based on a pre-defined central randomization scheme. An IRS User Guide will describe all steps for enrollment and randomization of the subjects.

As described in section 9.1, the duration of vision loss of each eye will be determined and documented at the Screening and Inclusion Visits (Visit 1 and Visit 2; for Visit 2 only if applicable in the setting of new onset vision loss in an eye previously unaffected by clinically manifested visual acuity loss Visit 1). The eye with the longest duration of vision loss will be the first affected eye and the eye with the shortest duration of vision loss will be the second affected eye. Eyes that have not yet experienced clinically manifested decline in visual acuity will be considered “not yet affected” eyes and have a value of zero days for vision loss duration. Subjects reporting simultaneous onset of vision loss in both of their eyes will have an equal vision loss duration for both eyes.

Subjects meeting all eligibility criteria for selection and inclusion will be randomized to treatment arm 1 (TARM1) or treatment arm 2 (TARM2) in a 1:1 allocation (see Figure 1). Subjects in TARM1 will receive intravitreal GS010 in their first affected eye and their second affected/not yet affected eye. Subjects in TARM2 will receive GS010 in their first affected eye and placebo intravitreal injection in their second affected/not yet affected eye.

Subjects with non-simultaneous onset of vision loss, for which a first affected eye and a second affected/not yet affected eye are designated based on non-equal vision loss duration, will be randomly allocated to TARM1 or TARM2 via the IRS system.

Subjects with simultaneous onset of vision loss in both eyes (i.e. equal vision loss duration for both eyes) will first be randomly allocated to TARM1 or TARM2 via the IRS system. Subsequently, for these subjects, the right or left eye will be randomly selected to serve as the second affected/not yet affected eye. If the right eye is selected randomly as the second affected/not yet affected eye, the left eye will be designated as the first affected eye, and vice versa.

### 13.10.1 Determination of the Best- and Worst-Seeing Eye

At Inclusion Visit (Visit 2), the best-seeing and worst-seeing eyes of each subject will be determined, based on the baseline vision testing performed at Visit 2. This will allow for assessment of the presence of a difference of the treatment effect in best- and worst-seeing eyes. A pre-defined algorithm for determining the best- and worst-seeing eyes will be utilized as follows:

1. LogMAR BCVA: On-chart eyes and off-chart eyes will have a LogMAR BCVA per the study's SOP for visual acuity testing. The eye of the subject with the better (i.e. lower or more negative) LogMAR BCVA will be the better-seeing eye of the subject. If both eyes have an equal LogMAR acuity the second criterion will be utilized.
2. SD-OCT parameters (to be used if there is no inter-eye difference based on Criterion 1):
  - i. The initial SD-OCT parameter will be the total volume of the RGC layer of the ETDRS macula area. The better-seeing eye will have the greater volume and quadrant thickness, unless there is macula edema. A difference of  $\geq 5\%$  is considered significant to determine greater volume.
  - ii. The second SD-OCT parameter (to be used if there is no inter-eye difference in criteria 2i) will be the combined volume of the RGC layer of the inner and outer nasal quadrants of the macula. The better-seeing eye will be the eye with greater volume. A difference of  $\geq 5\%$  is considered significant to determine greater volume.
3. Log of Contrast Sensitivity (LogCS) obtained with the Pelli Robson Low Vision Contrast Sensitivity Chart (to be used if there is no inter-eye difference in criteria 1 or 2). The eye with the best LogCS score is the better-seeing eye.
4. If the eyes are equal based on criteria 1 through 3, the best-seeing eye will be based on the subject's opinion.

### 13.11 Masking

Masking of both the subjects and the investigation team for the primary analysis, will be accomplished using a placebo intravitreal injection and the randomized allocation of treatment for second affected/not yet affected eyes. Only the pharmacist and the pharmacy team will be aware of the treatment allocation. All other study personnel, including but not limited to, the Investigator, designees or delegates of the Investigator (except the pharmacist/pharmacy team), the physician and allied health professionals performing the IVT injection of the IMPs (GS010 and placebo), and the ophthalmic technicians/orthoptists/optometrists or other study personnel performing the visual tests and ocular examinations, will be masked to treatment allocation.

To maintain the integrity of the ongoing study, individuals who are directly involved in study conduct and data management (e.g., personnel at investigational sites, Medical Safety Physician, Clinical Operations, and Data Management at CRO and Sponsor level) will be kept masked to the treatment allocation up to Visit 12 (Year 1.5). The Sponsor and CRO will be formally unmasked for the primary efficacy analysis at 1.5 years (Week 78) to allow an early registration if results meet the expectations.

Unmasked individual pharmacovigilance CRO personnel may know the treatment allocation of a given subject. No Sponsor or CRO personnel in charge of the conduct of the study (e.g. CRA, data manager, study manager) will have access to treatment information.

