## 12.4 Quality of Life Assessments

QoL questionnaires will be administered in paper version at the study site. An interviewer will administer the questionnaire to the subject. QoL questionnaires must be performed prior to any vision or ocular testing.

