### 16.2 Sample Size

Sample size calculation is based on the primary endpoint which is the change from baseline to 1.5 years post-treatment of the visual acuity (LogMAR). Masked preliminary data of the Phase III RESCUE and REVERSE sham-controlled studies of GS010 and monitored data from the Phase I/IIa safety and tolerability study of GS010 are used to estimate the standard deviation of the change from baseline to each available visit. These data do not take into account a potential treatment effect in the RESCUE and REVERSE studies and if there is an effect the standard deviation may be over-estimated.

From this masked preliminary analysis, a SD of 0.55 LogMAR has been estimated for the LogMAR change from baseline; this is reduced to 0.50 with the inclusion of baseline LogMAR as a covariate. Using this reduced value for SD and a treatment effect of 0.3 LogMAR in the change from baseline, the requested sample size to reach a power of 80% ( $\alpha = 0.05$  two-sided) according to an ANCOVA model including the baseline LogMAR value as covariate has been estimated, using SAS PROC POWER, to be 45 evaluable subjects per treatment group (i.e. 90 subjects in total).

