#### *16.4.1.10 Primary Significance Level*

The analysis will be performed using a significance level of 0.05 (two-sided).

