2.2. Secondary objectives

The efficacy objectives listed below will be analyzed for the second-affected/not-yet-affected eyes as the main eye of interest (designated the primary eye). Exploratory efficacy analyses will be conducted for the first affected eyes, but those analyses are secondary to any analysis on the primary eye, which is the second- affected/not-yet-affected eye.

1. To assess the safety and tolerability of bilateral and unilateral intravitreal injection of GS010.
2. To compare the time course of the BCVA LogMAR response in second-affected/not-yet-affected eyes treated with GS010 compared to placebo treatment.
3. To assess, at 1.5, 2, 3, 4 and 5 years post-treatment, the efficacy of intravitreal GS010 compared to placebo intravitreal injection in second-affected/not-yet-affected eyes, by determining the difference in the rate of responder eyes.
4. To compare the time course of the response in second-affected/not-yet-affected eyes treated with GS010 compared to placebo treatment and to estimate the magnitude of the treatment effect at 1.5, 2-, 3-, 4- and 5-years post-treatment, with parameters measured by:
 - a. Spectral-Domain Optical Coherence Tomography (SD-OCT);
 - b. Humphrey Visual Field (HVF)30-2;
 - c. Pelli-Robson Low Vision Contrast Sensitivity (CS).
5. To verify whether a difference exists at 1.5, 2, 3, 4 and 5 years post-treatment, between first affected eyes and second-affected/not-yet-affected eyes treated with GS010, using both an intra-subject and inter-subject analysis, with
 - a. LogMAR BCVA
 - b. Parameters measured by SD-OCT
 - c. Parameters measured by HVF 30-2, and
 - d. Parameters measured with Pelli Robson Low Vision Contrasts Sensitivity.

6. To assess, at 1.5, 2, 3, 4 and 5 years post-treatment, the rate of responders in first affected eyes treated with GS010.
7. To assess humoral and cellular immune responses to Adeno-Associated Virus vector 2 (AAV2) after unilateral and bilateral intravitreal administration.
8. To assess the impact of bilateral intravitreal GS010 administration on Quality of Life (QoL) scales at 1.5, 2-, 3-, 4- and 5-years post-treatment.

3. Study design

GS-LHON-CLIN-05 is a Phase III, global, multicenter, randomized, double-masked for the primary analysis, placebo-controlled, clinical study. As LHON is a neurodegenerative disease, the goal is to administer GS010 as soon as possible upon confirmation of the LHON diagnosis and the causative mutation.

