3.7. Post-treatment follow-Up period analyses

All planned analyses identified in this SAP will be performed by IQVIA Biostatistics following an interim database lock. The final analyses for the Post-Treatment Follow-Up Period 1 will be performed when all subjects have completed Visit 13, 2 years post dose. Three additional analyses will be performed when all subjects have completed Visit 14 (3 years post dose), Visit 15 (4 years post dose), and Visit 16 (5 years post dose). All efficacy analyses performed when all subjects have completed Visits 13, 14, 15, and 16 (i.e. 2-, 3-, 4-, and 5-years post dose) are considered secondary and will be supportive of the primary efficacy analysis.

4. Analysis populations

Agreement and authorization of subjects' inclusion/exclusion from each analysis set will be conducted prior to the unmasking of the study.

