4.5. Per Protocol-5Y population (PP5Y)

The Per Protocol (PP) population at 5 years will consist of all subjects in the Per Protocol population who did not receive Idebenone after Year 1.5 visit. This population is supportive of the ITT analysis population for the 5Y analyses.

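### Masking of examiners, interviewers and subjects is not assured after Visit 12, yet the arms are compared on effort-dependent outcomes up to Year 5

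*Protocol*

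**What the plan says.** **Masking.** Protocol 13.11 states that those directly involved in conduct, with site personnel named among them, "will be kept masked to the treatment allocation up to Visit 12 (Year 1.5". The same section describes masking of subjects and the investigation team as being for the primary analysis, as does the design statement in Protocol 9.1. It names the Sponsor and CRO as the parties unmasked at 1.5 years.

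**Outcomes measured afterwards.** The schedule in Protocol 9.2 continues visual acuity, contrast sensitivity, Humphrey visual field, VFQ-25 and SF-36 through Visit 16. On the questionnaires, Protocol 12.4 adds: "An interviewer will administer the questionnaire to the subject".

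**Comparisons made afterwards.** One secondary objective in SAP 2.2 is "To assess, at 1.5, 2, 3, 4 and 5 years post-treatment, the efficacy of intravitreal GS010 compared to placebo intravitreal injection", by responder rate. SAP 13.2.3 specifies, up to 5 years, a separate ANCOVA for LogMAR change at each visit and logistic models for response. It applies MMRM to SD-OCT, visual field, contrast sensitivity, VFQ-25 and SF-36, with no stated cut at 1.5 years for those endpoints. SAP 3.7 says that the analyses at 2 to 5 years "are considered secondary and will be supportive of the primary efficacy analysis".

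**The concern.** Acuity, contrast sensitivity and visual field depend on the subject's effort and the examiner's encouragement. The questionnaires depend on opinion and are taken by interview. The arms differ only in whether the second affected eye received GS010 or placebo. A subject, examiner or interviewer who knows which eye had placebo could therefore shift these measurements by arm.

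A between-arm difference that appears or grows after Year 1.5 would then have two possible explanations: GS010 or knowledge of allocation. This matters because sustained efficacy is one of the two reasons that Protocol 6.2.7 gives for extending follow-up to 5 years; the other is delayed safety. The SAP has no label, split or sensitivity analysis by masking status that would let a reader separate the two explanations.

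**Working it through.** **1. What the sections say about masking after Visit 12**

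| Section | Who | End point |
|---|---|---|
| Protocol 13.11, second paragraph | Site personnel, clinical operations, data management | Visit 12 (Year 1.5) |
| Protocol 13.11, last paragraph | Sponsor and CRO conduct staff have no access to treatment information | None given |
| Protocol 9.1 | Subjects are double masked | None given, but the design is masked for the primary analysis |
| Protocol 13.12 | Allocation revealed only for clinical care and safety | None given |
| Protocol 16.4.1.15 and 16.4.1.17; SAP 3.6 and 13.1.2 | The study as a whole is unmasked | 1.5-year analysis |

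The only dated commitment covering sites ends at Visit 12. The open-ended statements point towards continued masking. The statements that the study is unmasked do not say whether sites and subjects are included. Within 13.11, conduct staff are masked to Visit 12 in one paragraph and without limit in another. Status at Years 2 to 5 is thus unstated rather than stated to be open.

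**2. How much follow-up is exposed**

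Post-treatment visits are Visits 4 to 16, which is 13. Those after day 548 are on days 730, 1,095, 1,460 and 1,825, which is 4. In time, 5 − 1.5 = 3.5 years.

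**3. Which visits precede study-level unmasking**

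Inputs are the first screening visit in March 2018, screening 7 to 28 days before treatment, and the last Visit 13 in Q3 2021 (Protocol 9.1.2 and 9.2). Assume target-day visits, uniform accrual and no unmasking before the last Visit 12.

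- First treatment: 8 March to 28 April 2018.
- Last treatment: Q3 2021 − 730 days = 2 July to 1 October 2019.
- Last Visit 12: + 548 days = 31 December 2020 to 1 April 2021.
- Accrual span: 430 to 572 days.
- Year 2 visits before the last Visit 12: 1 − (730 − 548)/span = 1 − 182/430 = 58% to 1 − 182/572 = 68%.
- The first Year 3 visit falls in March or April 2021, so Years 3 to 5 fall almost wholly afterwards.

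If Visit 12 instead meant each subject's own visit, the first subject would reach it between 7 September and 28 October 2019. That is 430 to 572 days, or about 14 to 19 months, before the last subject does.

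**4. Sensitivity of a later acuity comparison**

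First, the plan's own figure. With "a treatment effect of 0.3 LogMAR in the change from baseline", SD 0.50, two-sided 0.05 and 80% power, the normal approximation gives 44 per arm. The noncentral t with 2n − 3 degrees of freedom gives power of 79.5% at 44 and 80.4% at 45, so the stated 45 is reproduced.

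Now take 45 per arm, no true effect, and an **assumed** between-arm expectation bias b, using 0.02 LogMAR per letter (Protocol 12.5.2). The standard error is 0.50 × √(2/45) = 0.105, and the noncentrality is b/0.105.

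| Assumed bias | LogMAR | Chance of p < 0.05 |
|---|---|---|
| 1 letter | 0.02 | 5.4% |
| 2 letters | 0.04 | 6.6% |
| 3 letters | 0.06 | 8.7% |
| 5 letters | 0.10 | 15.5% |
| 10 letters | 0.20 | 46.7% |

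The documents give no estimate of such a bias.

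**5. Status of the later results**

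Protocol 16.4.1.16 calls the Year 2 to 5 efficacy analyses exploratory, though also supportive of the primary. Protocol 16.4.2.7 plans no hypothesis testing in the follow-up population. SAP 3.7 calls the later analyses secondary, and SAP 13.2.3 fits comparative models to Year 5 (on the ITT population, by SAP 13.2). SAP 6.3 spends all alpha on the primary endpoint.

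**The case against.** A reader might infer that sites and subjects were told the allocation after Visit 12, so that later data were collected open-label. The documents do not say so. Only the Sponsor and CRO are named as unmasked, and Protocol 9.1 and 13.12 carry undated wording against disclosure. This stands, and it limits the point to masking that is not assured.

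A reader might also take Visit 12 as each subject's own visit, opening allocation 14 to 19 months before the last primary assessment. Protocol 16.4.1.15 and 16.4.1.17 and SAP 13.1.2 place the primary analysis after the last subject's 1.5-year assessment, with an interim lock. No section provides for release subject by subject. This is only a wording risk.

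Nor does the SAP pool earlier and later acuity in one model. Its LogMAR MMRM stops at 1.5 years (SAP 13.1.6); only the protocol's trend model (16.4.2.4.2) has no end time. The other MMRMs include treatment by visit, so each visit has its own contrast. A masking-period term would add nothing if status changed at the same visit for everyone.

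Idebenone use is partly addressed: a supportive 5-year analysis is limited to per-protocol subjects "who did not receive Idebenone after Year 1.5 visit". No section links such use to knowledge of allocation.

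Finally, the later results have declared limits, and SAP version 10.0 is dated October 2024, when the last visit was already expected (Q3 2024). An amendment may come too late to change conduct. That weakens the conduct part of the remedy but not the reporting part.

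**Conclusion.** The point holds as a gap in assurance. Masking of examiners, interviewers and subjects at Years 2 to 5 is neither secured nor consistently described, while the SAP compares arms on outcomes that such knowledge can influence and gives the results higher standing than the protocol does. Up to 4 of 13 post-treatment visits are affected. Under study-level unmasking and the accrual assumption above, roughly a third to two fifths of Year 2 visits (32% to 42%) and nearly all Year 3 to 5 visits are exposed. SD-OCT is less open to this problem than the effort- and opinion-dependent measures.

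The size of any bias is unknown; the rejection rates above show sensitivity only. The 1.5-year primary test and the sample size are unaffected, provided that unmasking is study-level. The change is worth making because it is cheap and protects the durability comparison.

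**What to change.** - Amend Protocol 13.11 so that subjects, and all site staff who perform or score acuity, contrast sensitivity, visual field and quality of life, stay masked through the last Visit 16. Unmask only a firewalled sponsor/CRO analysis team, after the last subject's Visit 12 and the interim lock. Leave the 13.12 route unchanged.
- State that Visit 12 means the last subject's Visit 12, and bring the undated sentences in 9.1, 13.11 and 13.12 and the study-level statements in 16.4.1.15 and 16.4.1.17 into line.
- Record the date of any unmasking of a subject or assessor. Repeat the Year 2 to 5 comparisons without values obtained after that date, and label the results by masking status. For Year 2, where status may differ between subjects, the dates are what make this possible.
- Reconcile Protocol 16.4.1.16 and 16.4.2.7 with SAP 3.7 and 13.2.3 on whether the later results are exploratory or secondary, and whether they are tested.

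The cost is protocol and SAP wording, a firewall around the 1.5-year results, and later disclosure of allocation to subjects and sites. If follow-up has already ended, the recording (from existing unmasking records), labelling, re-analysis and reconciliation can still be done.
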